## 1.3 Venetoclax

Venetoclax (also referred to as ABT-199 and GDC-0199) is a novel, orally bioavailable, smallmolecule B-cell lymphoma-2 (BCL-2) family inhibitor in the biarylacylsulfonamide chemical class. Venetoclax binds with high affinity (inhibition constant [Ki] < 0.010 nM) to antiapoptotic protein BCL-2 and with lower affinity to other antiapoptotic Bcl -2 family proteins, like Bcl-XL and Bcl-w (> 4,000-fold and > 2,000- to > 20,000-fold lower affinity than to BCL-2, respectively).

Antiapoptotic BCL-2 family members are associated with tumor initiation, disease progression, and chemotherapy resistance, as well as autoimmunity. Overexpression of BCL-2 is a major contributor to the pathogenesis of some lymphoid malignancies; antagonism of the action of these proteins may enhance response to therapy and overcome resistance, and thus, these proteins are compelling targets for anti-tumor therapy (Fesik, Nat Rev Cancer 2005).

### 1.3.1 Summary of data

Venetoclax is a novel, orally bioavailable, small molecule BCL-2 family inhibitor in the biarylacetylsulfonamide chemical class. Venetoclax binds with high affinity ( $K_i < 0.010$  nM) to antiapoptotic protein BCL-2 and with lower affinity to other antiapoptotic BCL-2 family proteins, like Bcl-XL and Bcl-w (> 4,000-fold and > 2,000-fold to > 20,000-fold lower affinity than to BCL-2, respectively). Venetoclax is projected to have a different safety profile than dual BCL-2/Bcl-XL inhibitors. Survival of platelets depends on BCL-XL and thrombocytopenia is therefore a major DLT caused by inhibition of BCL-XL in the clinic. Venetoclax is expected to yield an improved therapeutic index by maintaining efficacy against tumor cells while avoiding dose-limiting thrombocytopenia.

Nonclinical and clinical data available with venetoclax are summarized below.

Oncology non-clinical pharmacology: In vitro, venetoclax demonstrated cell killing activity against patient-derived CLL and AML cells and a variety of lymphoma and leukemia cell lines, including B-cell FLs, MCLs, DLBCLs, AMLs, and MM. Venetoclax was especially potent against NHL cell lines expressing high levels of BCL-2. Venetoclax inhibits subcutaneous xenograft growth of human tumor cell lines derived from ALL, NHL, and AML, and is highly efficacious using various doses and combined with other regimens. The drug is also active in a model of disseminated ALL and AML.

Non-clinical safety pharmacology: Venetoclax was tested in a battery of safety pharmacology assays and produced no effects in CNS/neurobehavioral, or respiratory studies in mice at oral doses up to 600 mg/kg. In dogs, mild reductions in cardiac contractility and cardiac output were observed at plasma concentrations of  $\geq 16$   $\mu\text{g/mL}$ ; concentrations greater than the concentration of venetoclax in humans (average  $C_{\text{max}} = 6.09$   $\mu\text{g/mL}$  at the 1200 mg dose). However, no effects on blood pressure, heart rate, or ECG parameters were observed in dogs at a maximum drug concentration of 46  $\mu\text{g/mL}$ .

Non-clinical product metabolism: Venetoclax exhibited moderate permeability in the Caco-2 assay. In rats, venetoclax was widely distributed into liver, kidneys, spleen, heart, lungs, small intestine, and white fat, but was poorly distributed in testes, brain, muscle, bone, and pigmented tissues. Venetoclax showed moderate in vitro metabolic stability in hepatic systems across species tested, with the exception of dog hepatocytes, where stability was low to moderate. In rats, 14.3% of the dose was recovered as parent drug after 48 hours post-dose, while 76.9% of the dose was excreted as metabolites in bile. Profiles in bile indicated that metabolism was the major clearance mechanism, while biliary excretion of parent drug played a secondary role in drug elimination.

Biotransformation of [H] venetoclax proceeded via a combination of oxidation and conjugation. Venetoclax is predominately metabolized by CYP3A4 in vitro, thus CYP3A4 inhibitors or inducers are expected to cause changes in venetoclax exposure. Clinical studies have supported the in vitro observations for venetoclax as a sensitive substrate of CYP3A4: > 5-fold increase in AUC when co-dosed with ketoconazole, and > 50% decrease in AUC when co-dosed with rifampin. At the 400 mg QD dose venetoclax is not predicted to be perpetrator of the major CYP enzymes, but venetoclax may weakly inhibit UGT1A1. Venetoclax is substrate for the efflux transporters P-gp and BCRP, and inhibitors or inducers of these transporters are expected to cause change in the exposure of venetoclax. Venetoclax is P-gp and BCRP inhibitor and may interact with substrates for these transporters. Venetoclax may inhibit OATP1B1 and cause weak interaction with drugs that are substrates of this transporter.

Non-clinical toxicology: The primary toxicities associated with repeat-dose administration of venetoclax were effects on the hematologic system (decreased lymphocytes and RBC mass in mice, rats and dogs), the male reproductive system (testicular germ cell depletion in dogs) and embryofetal toxicity in mice. Other noteworthy findings were epithelial single cell necrosis in multiple tissues and hair coat color change, both in dogs. For lymphocyte reductions, B cells were the most sensitive lymphocyte subtype based on the magnitude of decrease and/or the length of time required for recovery. Decreases of lymphocytes were reversible or partially reversible; decreases in erythrocytes were reversible. Venetoclax resulted in increased post-implantation loss and decreased fetal body weights in the mouse embryofetal development study at the highest dosage administered (150 mg/kg/day); the NOAEL was defined at the mid-dose of 50 mg/kg/day. Venetoclax was not teratogenic, and there were no other effects on development or fertility. Venetoclax was also negative in an in vivo phototoxicity assessment. In vitro genotoxicity studies (Ames and chromosome aberration assays) conducted on a major human metabolite.

Clinical pharmacokinetics: The venetoclax formulation currently used in clinical studies is a tablet formulation with strengths of 10, 50, and 100 mg. Following multiple-dose administration, the maximum plasma concentration of venetoclax was attained 5 to 8 hours after dosing. The harmonic mean terminal half-life (t1/2) ranged from 17 to 41 hours following a single oral dose of venetoclax. In subjects with CLL, venetoclax showed minimal accumulation, and steady-state AUC increased proportionally over the dose range of 150 to 800 mg. Venetoclax has been administered with food in all clinical studies, as food increased the bioavailability of venetoclax by approximately 3 - to 5-fold. Venetoclax is highly bound to plasma proteins with unbound fraction (fu) < 0.01, and it is primarily eliminated as metabolites in feces with negligible renal elimination (< 0.1%). Additionally, based on the population pharmacokinetic analysis, age, sex, race, weight, mild or moderate hepatic and renal impairment do not have an effect on venetoclax clearance.

Clinical safety and efficacy: A total of 1662 subjects have been exposed to at least 1 dose of venetoclax in the oncology and immunology development programs. A total of 1498 oncology subjects had data available in AbbVie and Genentech/Roche studies as of 28 November 2015. Of these 1498, 935 subjects had CLL/SLL, 346 subjects had NHL, 115 subjects had MM, 102 had AML; an additional 66 subjects were healthy volunteers. A total of 564 oncology subjects received the drug as monotherapy and 933 received the drug in combination with other therapies (rituximab, obinutuzumab, R-CHOP, G-CHOP, BR, BG, bortezomib plus dexamethasone, azacitidine, decitabine, and cytarabine).

Important identified risks are TLS and neutropenia, particularly in CLL indication. Infection is a potential risk. Other adverse events commonly observed with venetoclax include nausea, diarrhea, and other hematological effects (including, anemia, thrombocytopenia, and lymphopenia). Decreased spermatogenesis has been observed in non-clinical studies with dogs, effect in humans is unknown. In addition, as venetoclax is being evaluated in subjects with relapsed/refractory disease who had previously been treated with various cytotoxic agents, second primary malignancies are closely monitored.

In subjects with AML, the ORR was 19% for venetoclax monotherapy (Study M14 -212) and was 77% for venetoclax in combination with azacitidine or decitabine (Study M14 -358).

### **1.3.2 Guidance for investigators**

On the basis of non-clinical data and previous experience with BCL-2 inhibitors, as well as the available preliminary data in the venetoclax clinical oncology program, the following guidance is provided for the investigator.

#### **Contraindications**

Concomitant use of venetoclax with strong and moderate CYP3A inhibitors at initiation and during the dose titration phase is contraindicated ([section 5.5](#)).

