### **Concomitant Use with Other Medications**

During Phase I/Escalation part, strong and moderate CYP3A inhibitors and inducers (see [Appendix 1](#)) are prohibited.

If a patient critically needs e.g. anti-fungal treatment **after** the end of the venetoclax treatment period, that should be discussed with the coordinating investigator and the decision should be made based on the medical/clinical need.

For Phase II/Expansion part, the concomitant use of strong and moderate CYP3A inhibitors is allowed, but the dose of venetoclax should be reduced as described in section [5.5](#).

Venetoclax should be administered using caution with substrates or inhibitors of P-gp, BCRP, or substrates of OATP1B1/B3. If venetoclax is co-administered with warfarin, the international normalized ratio (INR) should be monitored closely.

Live-virus vaccines should not be given within 28 days prior to the initiation of study treatment, at any time during study treatment, or in the 30 days following last dose of study treatment.

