**4.2 Exclusion criteria**

- Acute promyelocytic leukemia (AML M3)
- CNS involvement or subjects with extramedullary disease only
- Known hypersensitivity to excipients of the preparation or any agent given in association with this study including cytarabine or mitoxantrone
- Intended hematopoietic stem cell transplantation planned as early conditioning from aplasia without previous blood count recovery

- Cumulative previous exposure to anthracyclines of >410 mg/m^2 doxorubicin equivalents
- Acute GVHD ≥ grade 2, extensive chronic GVHD or requiring systemic immunosuppressive therapy within 2 weeks prior to start of study treatment
- HIV infection (due to potential drug-drug interactions between antiretroviral medications and venetoclax, as well as anticipated venetoclax mechanism-based lymphopenia that may potentially increase the risk of opportunistic infections).
- Inability to swallow oral medications
- Any malabsorption condition
- Treatment with strong and moderate CYP3A inhibitors (see [Appendix 1](#)) during screening
- Cardiovascular disability status of New York Heart Association (NYHA) Class ≥ 2.  
Class 2 is defined as cardiac disease in which patients are comfortable at rest but ordinary physical activity results in fatigue, palpitations, dyspnea, or anginal pain.
- Chronic respiratory disease that requires continuous oxygen use.
- White blood cell count > 25 × 10^9/L. Note: Hydroxyurea is permitted to meet this criterion.
- AML relapse treatment with any investigational or commercial drug within 14 days before enrolment. Hydroxyurea is allowed until enrolment to control peripheral WBC counts. Toxic effects of previous investigational drug treatment have to recover to Grade <2.
- Substance abuse, medical, psychological, or social conditions that may interfere with the subject's cooperation with the requirements of the trial or evaluation of the study results
- Pregnant or breastfeeding women.  
Breastfeeding has to be discontinued before onset of and during treatment and should be discontinued for at least 3 months after end of treatment.
- History of active or chronic infectious hepatitis unless serology demonstrates clearance of infection  

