#### Expansion Phase:

For the phase 2 part of the protocol, the below dose modification according to the following [Table 8](#) is recommended in case of co-administration with strong / moderate CYP3A inhibitors.

Table 8: Venetoclax in case of strong and moderate CYP3A inhibitors

Inhibitors	Initiation and Ramp-Up	Venetoclax Daily Dose (after Ramp-Up)
Strong CYP3A inhibitor	Day 1 – 10 mg Day 2 – 20 mg Day 3 – 50 mg Day 4 – 100 mg or less	100 mg or less
Moderate CYP3A inhibitor (reduce the Venetoclax dose by at least 50%)	Day 1 – 20 mg Day 2 – 50 mg Day 3 – 100 mg Day 4 – 200 mg	200 mg

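### For phase II, section 1.3.2 contraindicates strong and moderate CYP3A inhibitors during venetoclax initiation and titration, while section 5.5 gives a day 1–4 ramp-up schedule for use with them

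*Protocol*

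**What the plan says.** **General guidance.** Section 1.3.2, Contraindications, reads: "Concomitant use of venetoclax with strong and moderate CYP3A inhibitors at initiation and during the dose titration phase is contraindicated". It is not limited to a phase and refers the reader to section 5.5.

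**Phase I.** Section 1.3.2, Concomitant Use with Other Medications, prohibits these drugs in escalation (the sentence begins "During Phase I/Escalation part, strong and moderate CYP3A inhibitors and inducers"). Table 7 in section 5.5 likewise excludes them in the escalation phase.

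**Phase II.** The same part of 1.3.2 continues: "For Phase II/Expansion part, the concomitant use of strong and moderate CYP3A inhibitors is allowed, but the dose of venetoclax should be reduced", with a reference to section 5.5. Section 5.4.2 gives the ramp-up and then requires venetoclax dose modification when posaconazole or another strong or moderate inhibitor is co-administered. Table 7 lists these inhibitors as cautionary in expansion and maintenance, with dose reduction. Section 5.5 then introduces Table 8 ("For the phase 2 part of the protocol, the below dose modification according to the following" ... "is recommended in case of co-administration with strong / moderate CYP3A inhibitors"). Its first dosing column is headed "Initiation and Ramp-Up" and covers days 1 to 4.

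**Eligibility.** Section 4.2 lists as an exclusion "Treatment with strong and moderate CYP3A inhibitors" during screening, without a phase limit.

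**The concern.** Section 1.3.2 sends the reader to section 5.5 for a contraindication that 5.5 does not contain for phase II. What 5.5 contains instead is a dosing schedule for the combination on the very days concerned. A site that relies on the Contraindications paragraph would not co-administer on days 1 to 4. A site that relies on Table 8 would co-administer with a lower venetoclax ramp-up. Both could say that they followed the protocol.

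These days matter for safety. Section 5.4.1 says that the ramp-up is there to mitigate the risk of tumor lysis syndrome. Section 1.3.1 reports a more than 5-fold rise in venetoclax AUC with ketoconazole, which Appendix 1 lists as a strong inhibitor. Section 5.4.5 simplifies the prophylaxis for tumor lysis in the expansion part, where the conflict lies. Opposite instructions also mean that co-medication and venetoclax dose in the first days could differ between sites for no clinical reason.

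**Working it through.** The point is mainly a comparison of texts. The arithmetic only shows what the conflict does and does not affect.

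**1. Passages side by side**

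| Place | Phase | Initiation and ramp-up with a strong or moderate inhibitor |
|---|---|---|
| 1.3.2, Contraindications | none named | contraindicated; refers to 5.5 |
| 1.3.2, Concomitant Use | I | prohibited |
| 1.3.2, Concomitant Use | II | use allowed at reduced dose per 5.5; ramp-up not named |
| 5.4.2 | II | dose modification required per 5.5, stated directly after the ramp-up |
| 5.5, Table 7 | I | excluded |
| 5.5, Table 7 | II and maintenance | cautionary, dose reduction necessary |
| 5.5, Table 8 | II | day 1–4 doses given |
| 4.2 | none named | treatment during screening excludes |

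For phase I the rows agree. For phase II, every trial-specific row allows co-administration, and only the first row forbids it during titration. Section 4.2 concerns screening, which is day -14 to -1 in Table 9, whereas Table 8 starts on day 1. Both can hold for an inhibitor started on or after day 1.

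**2. Table 8 covers the same days as the standard ramp-up (Table 2)**

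| Day | Table 2 | Strong | Lower by | Moderate | Lower by |
|---|---|---|---|---|---|
| 1 | 50 mg | 10 mg | 80% | 20 mg | 60% |
| 2 | 100 mg | 20 mg | 80% | 50 mg | 50% |
| 3 | 200 mg | 50 mg | 75% | 100 mg | 50% |
| 4 | 400 mg | 100 mg or less | at least 75% | 200 mg | 50% |
| Sum | 750 mg | at most 180 mg | | 370 mg | |

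Table 8 is therefore a schedule for the initiation and titration days themselves.

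**3. Does the conflict decide who enters the per-protocol set?** Section 8.2.2.2 takes its dose minimum from 3.2.1, which for venetoclax is at least 3800 mg. The totals below assume the 14-day schedule and 100 mg as the strong-inhibitor dose from day 4.

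- Standard: 50 + 100 + 200 + 11 × 400 = 4750 mg.
- Inhibitor on days 1–4 only: strong 180 + 10 × 400 = 4180 mg; moderate 370 + 10 × 400 = 4370 mg. Both are above 3800 mg.
- Inhibitor from day 5 only: strong 750 + 10 × 100 = 1750 mg; moderate 750 + 10 × 200 = 2750 mg. Both are below 3800 mg.
- Inhibitor on all 14 days: strong 10 + 20 + 50 + 11 × 100 = 1180 mg; moderate 20 + 50 + 100 + 11 × 200 = 2370 mg. Both are below 3800 mg.

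The disputed days account for 750 − 180 = 570 mg (570/4750 = 12%) or 750 − 370 = 380 mg (380/4750 = 8%). The shortfall against 3800 mg comes from the dose after ramp-up, which the Contraindications sentence does not address.

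**The case against.** The best case for leaving the text alone is that the Contraindications sentence is general guidance placed before the trial-specific rules. The phase II rules agree with one another: 1.3.2 on concomitant use, 5.4.2, Table 7 and Table 8. The 1.3.2 paragraph that allows use reaches titration by its reference to 5.5, and section 5.1.2 provides 10 mg tablets for inhibitor-related reductions in expansion. A site that follows the sentence's own cross-reference arrives at an explicit phase II schedule. Moreover, neither reading has an inhibitor given with the full standard ramp-up: one has no inhibitor, the other has venetoclax cut by 75–80% or by 50–60%.

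Much of this stands. It would be too strong to say that a phase II site has no guidance, or that the protocol is inconsistent throughout. It does not remove the conflict. A contraindication is a safety statement in its own right, it carries no phase limit, and nothing in the protocol says that 5.5 overrides it. The paragraph allowing phase II use does not mention initiation or titration, so a careful reader could combine the two as allowed in phase II, but only after ramp-up. Table 8 contradicts that combination.

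A reader might also infer that the section 4.2 exclusion is a further contradiction. It is not, because it covers the screening period only. It does bear on when the initiation column of Table 8 can apply: only to an inhibitor started after screening.

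**Conclusion.** The point holds, and it is confined to phase II. One sentence in 1.3.2 contraindicates strong and moderate CYP3A inhibitors at initiation and titration. The phase II text, most directly Table 8, gives doses for that situation. The two cannot both apply on days 1 to 4. Its weight comes from being a safety instruction on the days meant to limit tumor lysis; no analysis figure is in error. This review does not judge which instruction is clinically right.

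A reader might infer that the conflict decides who enters the per-protocol set, since an inhibitor throughout gives at most 1180 mg or 2370 mg against a minimum of 3800 mg. The documents do not support that. Co-administration on the disputed days alone leaves 4180 mg or 4370 mg, while co-administration starting on day 5 falls short whichever way the conflict is settled. That shortfall is a separate issue between Table 8 and section 3.2.1. The per-protocol set also serves only a sensitivity analysis (8.2.5), and the full analysis set used for the primary test has no dose minimum (8.2.2.1). These totals assume 14 days of venetoclax without interruption or toxicity-related reduction.

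**What to change.** The sponsor should reconcile the Contraindications sentence in 1.3.2 with the concomitant-use paragraph of 1.3.2, section 5.4.2, Table 7 and Table 8. One statement per phase should say whether co-administration of strong or moderate CYP3A inhibitors during initiation and ramp-up is permitted, and all these places should follow it. The choice of rule is the sponsor's clinical decision. If the initiation column of Table 8 is kept, a short note should say how it fits with the screening exclusion in 4.2. In the same edit, the reference in Table 7 to Tables 8 and 9 needs checking, because Table 9 is the visit schedule.

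The cost is protocol wording in an amendment. No patients, procedures or analyses are added, and the sample size and primary test are unchanged.

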#### **Warning and Precautions**

The following sections are a summary of the identified and potential risks when dosing with venetoclax, and the specific safety measures that need to be taken.

##### Tumor Lysis Syndrome (Oncology Studies)

Tumor lysis syndrome (TLS) is an important identified risk for venetoclax in oncology studies, especially in CLL. As a result of on-target effects, the potential for TLS was identified early in the program. The available data suggest that in non-CLL subjects the risk of TLS is low. Since the

data set is small, the risk of TLS is being closely monitored in non-CLL indications. In general, before initiating venetoclax, subjects risk for developing TLS should be assessed. Prophylaxis with hydration and uric-acid reducing agents is recommended. Clinical chemistries should be corrected. Monitor with clinical chemistries and manage promptly, as clinically indicated. Please refer to detailed guidance for TLS management in section [5.4.5](#).

### Neutropenia

Neutropenia is an important identified risk for venetoclax, specifically in CLL. Clinical data from the oncology studies suggest that the neutropenia adverse events are observed among subjects who receive venetoclax as a single agent or in combination with other therapeutic agents, with slightly higher frequency observed in some combination studies.

### Infections

Infections have been reported in the oncology clinical studies; however, these events are confounded by the underlying disease, comorbidities, and other immunosuppressive medications. To date, no clear relationship has been noted between serious infectious events and neutropenia. The types of infectious events observed generally have been consistent with those anticipated in the elderly population of heavily pretreated subjects with hematologic malignancies and are similar across all indications.

### Other Hematological Effects

Anemia has been reported in the oncology studies with slightly higher frequency in some studies in which venetoclax is combined with other chemotherapeutic agents; however, most of the events were non-serious and confounded by disease factors and prior therapies. The dataset in non-CLL indications is small.

Thrombocytopenia adverse events have been reported in the oncology studies, with slightly higher frequency in studies in which venetoclax is combined with other chemotherapeutic agents. However, most of the events were non-serious and assessment of these events is confounded by the subjects' underlying disease state, prior therapies and preexisting thrombocytopenia, including autoimmune thrombocytopenia in several subjects. The dataset in non-CLL indications is small.

Lymphopenia has been observed in preclinical studies. While opportunistic infections have been reported in the clinical program, data is confounded by subjects underlying disease and prior therapies. In the oncology studies, anti-infective prophylaxis should be implemented as clinically indicated, including appropriate prophylaxis for viral, fungal, bacterial, or *Pneumocystis carinii* pneumonia infections.

